##### 2. Secondary Endpoints

1. To assess incident plaque rates and quantitative changes in different plaque types in patients randomized to warfarin vs. rivaroxaban using CTA, 12 months after an initial evaluation.
2. Evaluation of plaque progression rates and incident plaque rates in subjects treated with warfarin vs. rivaroxaban. In that context, we will:
  - a. determine whether subjects treated with rivaroxaban display slower rates of progression compared to warfarin treated subjects, after control for all CV risk factors and demographics

[figure not shown]
The study design calls for the enrollment of 120 eligible subjects of diverse ethnic population. Given dropout rate, at least 100 patients should be available for final analysis at the conclusion of 52 week follow-up. Baseline examination will include the results of their demographic, coronary risk factor, lab tests, coronary calcium, as well as coronary plaque volume/composition. All participants will be educated on a low-cholesterol diet at entry to the study. Baseline information regarding risk factors for atherosclerotic cardiovascular disease (cigarette smoking status, systemic hypertension, family history of premature atherosclerosis, menopausal and hormone replacement status in women, sedentary lifestyle, current medications, chest pain questionnaire and measures of obesity) will be determined. After randomization, participants will return quarterly (3, 6, 9 and 12 months to assess compliance with medication, and receive an additional supply of medicine. At 52 weeks follow up, coronary calcium and coronary plaque volume/composition will be measured by readers blinded to the randomization and clinical activities, who are not aware of study-group assignments

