### CAC and Progression

Multiple studies have been done to demonstrate the feasibility of measuring CAC change at 12 months. Initial studies suggested that treatment with statins was associated with slower progression of CAC. Callister et al.i studied 149 patients. Patients underwent a baseline and follow-up EBT scan at 12 months and serial LDL cholesterol measurements were obtained.

Progression of calcium volume score was seen in all untreated patients (n = 44; mean LDL 147 ± 22 mg/dl) and averaged 52 ± 36% per year. In contrast, the mean yearly calcium volume score change for all treated patients (n = 105; mean LDL 114 ± 23 mg/dl) was 5 ± 28% (p < 0.001 vs. untreated patients). Among the treated patients, 65 individuals attained a LDL level <120 mg/dl (mean LDL 100 ± 17 mg/dl) and showed a net regression of their calcium volume score (-7 ± 22%). In patients who received HMG-CoA reductase inhibitors but maintained an average LDL >120 mg/dl (mean LDL 139 ± 18 mg/dl), the mean yearly calcium volume score progression was 25 ± 22%. Similar one year studies by [name] et al.,ii and Achenbach et al.,iii showed that statin therapy is associated with slowing of progression of coronary calcium.

The BELLES trialiv was a prospective randomized study of 615 postmenopausal and dyslipidemic women randomized after initial CAC scan to atorvastatin 80 mg/day or pravastatin 40 mg/day. A second scan was repeated in 12 months. The attained mean LDL cholesterol level was significantly lower with atorvastatin (94 mg/dl) than pravastatin (129 mg/dl). Nonetheless, the median relative change in the calcium volume score was not different between the two treatment arms (15.1% and 14.3% for atorvastatin and pravastatin, respectively, p = NS).

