### B. Laboratory Measurements (0 , 6 and 12 months)

All participants will be instructed to abstain from smoking, alcohol, and food intake, eg, overnight fasting or at least 10 hours before sample drawing. Venous blood samples of all patients will be drawn after admission in a fasting state. Routine blood specimens will be shipped to our

central clinical laboratory to be measured uniformly in a highly standardized center. Blood samples, including CBC, Matrix Gla protein, and INR will be assessed at every visit.

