## 8. STUDY ASSESSMENTS AND PROCEDURES

### 8.1 Standard Safety Laboratory Panel

Hematology

- Hemoglobin
- Hematocrit
- Red blood cell count
- White blood cell count and differential
- Platelet count

Serum chemistry

- Aspartate Aminotransferase (AST, SGOT)
- Alanine Aminotransferase (ALT, SGPT)
- Alkaline Phosphatase (reflex to GGTP)
- Creatine Kinase (Creatine Phosphokinase) (CK) (CPK) (reflex to troponin)
- Total Bilirubin
- Uric Acid
- Blood Urea Nitrogen (BUN)
- Electrolytes - sodium, potassium, chloride, Total Protein, Albumin
- Serum Creatinine (Scr)

EGFR will be estimated by the method of **Cockcroft-Gault**:

Cockcroft-Gault CrCl =  $(140 - \text{age}) * (\text{Wt in kg}) * (0.85 \text{ if female}) / (72 * \text{Cr})$

The eGFR is expressed in mL/min/1.73m^2

- Females only: urine HCG pregnancy test (HCG minimum sensitivity of 25 IU/L). If a urine HCG test is positive, patient will be excluded

Data to be Collected: Routine demographic and cardiovascular clinical data have been collected for all patients in the study. For CAC, we will collect Agatston and Volume scores, number of lesions and density for each plaque. For CCTA-specific variables, we will quantify and characterize the following APCs by both manual and automated plaque characterization methods:

- Coronary artery plaque volume
- Non-calcified plaque volume
- Calcified plaque volume
- Plaque location
- Plaque length
- Plaque distribution
- Arterial remodeling
- Low attenuation plaque (Hounsfield unit density <30 HU)
- Spotty calcifications

*2b1a. Overview:* In a single session at baseline and followup, after phlebotomy and physical examination, each subject will receive sequential non-contrast followed by contrast scans. The entire scanning procedure will take approximately 30 minutes.

*Screening.* Subjects will be screened for contraindications for beta-blockers and nitroglycerin (PDE5 inhibitors). The desired heart rate for adequate image quality is  $\leq 70$  bpm. If the heart rate is above this level, a beta-blocker will be prescribed. If a beta blocker is contraindicated, a calcium channel blocker will be given instead.

*2b1b. Noncontrast scan:* This will be performed to measure CAC. Patients will be positioned within the scanner with ECG leads, and a rhythm strip will be viewed. After a scout film is obtained, standard calcium scoring imaging will be performed at the end of inspiration.

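### Secondary endpoint 2a promises control for all cardiovascular risk factors, but the plan lists no lipids, glucose or diabetes status, and its ANCOVA adjusts only for demographics and baseline calcium score

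*Combined protocol and SAP*

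**What the plan says.** Protocol section 4, under Secondary Endpoints, sets the aim of 2a: to determine whether patients on rivaroxaban "display slower rates of progression compared to warfarin treated subjects, after control for all CV risk factors and demographics". The parent item concerns rates of plaque progression and of new plaque.

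The same section describes what is recorded at entry. In general terms, "Baseline examination will include the results of their demographic, coronary risk factor, lab tests, coronary calcium, as well as coronary plaque volume/composition". It then itemises the risk factors: "cigarette smoking status, systemic hypertension, family history of premature atherosclerosis, menopausal and hormone replacement status in women, sedentary lifestyle, current medications, chest pain questionnaire", followed by measures of obesity.

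The Laboratory Measurements paragraph, headed 0, 6 and 12 months, states that "Venous blood samples of all patients will be drawn after admission in a fasting state" and specifies "overnight fasting or at least 10 hours before sample drawing". The assays it names are CBC, Matrix Gla protein and INR.

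Section 8.1 itemises the safety panel: haematology plus a chemistry list of liver enzymes, CK, bilirubin, uric acid, BUN and creatinine, with "Electrolytes - sodium, potassium, chloride, Total Protein, Albumin".

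Section 13 (Statistical analysis) specifies, for all measures, an ANCOVA controlling for baseline demographics and baseline CACS. A separate logistic model for an increased Agatston score names age, VKA duration, left atrial diameter, statins and ACE inhibitors.

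**The concern.** The words of 2a make a strong promise, and two things are needed to keep it: the risk factors must be recorded, and the model must contain them. Neither is secured. Lipid level, glycaemia and diabetes status are standard members of any list of cardiovascular risk factors, yet none is itemised. The plan makes the gap conspicuous, because patients fast before the draw and both arms are taught a low-cholesterol diet, but no lipid is measured.

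What is at stake is one secondary analysis and how it is described. If the plan is followed literally, the adjusted result for 2a will omit several major risk factors while the protocol describes it as controlled for all of them. Baseline values are also the hardest to repair later. The protocol describes no sample storage, so a lipid or glucose value that is not assayed at entry may not be recoverable at analysis.

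**Working it through.** The point rests on no power, sample size or alpha figure, so there is no number of the plan's to reproduce. The check is to read every place that lists data, assays or covariates and compare it with what 2a requires.

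**Data collected**

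- *Itemised baseline risk factors (section 4):* smoking, hypertension, family history, menopausal and hormone status, activity, medication, chest pain and obesity. No diabetes, lipids or glucose. VKA duration is not listed either, although section 13 uses it as a covariate.
- *Laboratory Measurements paragraph:* three named assays, none of them a lipid or glucose.
- *Section 8.1 panel:* an itemised chemistry list that extends to uric acid, CK and albumin but has no lipids, glucose or HbA1c.
- *Figure 2 (visit schedule):* routine bloods only, not itemised.
- *Generic wording:* section 4 mentions coronary risk factors and laboratory tests in general, and section 8.1 mentions routine demographic and cardiovascular clinical data. Either could cover a history of diabetes. Neither names a lipid or glucose value.

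**Model**

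- *ANCOVA for all measures:* demographics and baseline CACS. No smoking, hypertension, diabetes, lipid or statin term. For a plaque outcome, the baseline value of the plaque measure itself is not named.
- *Logistic model:* concerns an increased Agatston score, not the treatment comparison of plaque progression. It names statins but no lipid level, glucose or diabetes.
- *Interaction check with baseline laboratory values:* can use only what is assayed, so it too would exclude lipids and glucose.

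So 2a is undelivered on two separate counts. Adding the assays alone would leave the model unchanged. Changing the model alone would leave it without these variables.

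**What the omission costs under randomization**

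Leaving out a baseline covariate does not bias a randomized comparison. It leaves in the residual whatever variance the covariate would have explained, and it removes the means of adjusting for a chance difference between arms.

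How likely such a difference is can be shown only by assumption, since the documents give no prevalence. Take a binary factor such as diabetes with prevalence p and n patients per arm. The standard error of the difference in proportions is √(2p(1−p)/n).

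- n = 50, p = 0.20: √(2 × 0.16/50) = 0.080, so the chance of an arm difference of 10 points or more is about 21%.
- n = 50, p = 0.40: √(2 × 0.24/50) = 0.098, chance about 31%.
- n = 60, p = 0.20 to 0.40: about 17% to 26%.

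A visible imbalance would therefore not be surprising at this size. These are probabilities of imbalance, not estimates of how far the treatment effect would move. The standard error of the unadjusted comparison already allows for chance imbalance.

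**The case against.** The strongest defence has four parts.

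1. *Randomization protects the comparison.* This stands in full, and it is why the point concerns precision and accurate description rather than validity.
2. *The lists are not exhaustive.* The section 8.1 panel is a safety panel, the Laboratory Measurements paragraph introduces its assays as inclusions, and the generic wording in sections 4 and 8.1 could take in diabetes history. This stands for diabetes. It does not stand for lipids or glucose, which no wording in the study procedures names.
3. *Some of the missing material is already covered.* Current medication is recorded at baseline, medication changes are asked about at 3, 6 and 9 months, arms are compared on concomitant medication, and statins are a named covariate in the logistic model. VKA duration is also a named covariate there, which implies that it will be obtained. This largely stands. What remains is to itemise the VKA start date so that the covariate can be derived, and to put statin use into the model for 2a.
4. *The study calls its sample size exploratory, and 2a is one secondary analysis.* This limits the weight of the point. It does not remove the mismatch between what 2a says and what the data and model provide.

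**Conclusion.** The point holds as a mismatch between a stated secondary objective and the plan for meeting it. It is worth correcting, but it does not threaten the primary result. The conclusion assumes that the itemised lists and section 13 will be followed as written, and that the generic wording adds at most a history of diabetes.

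Three stronger readings are tempting, and the documents support none of them.

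- *That 2a cannot be met at all.* It cannot be met from the items the plan lists. The generic wording leaves open that diabetes history is recorded.
- *That the omission biases the treatment effect, or that an LDL difference arising during the open-label year should be adjusted away.* Randomization deals with the first. LDL during follow-up is a post-randomization variable, and adjusting for it could distort the comparison.
- *That the background section lets one size the loss.* In the observational statin cohort under CAC and Progression, annual change was −7 ± 22% in treated patients with LDL below 120 mg/dl and 25 ± 22% above, a gap of 25 − (−7) = 32 points. That gap is by LDL attained on treatment, not baseline LDL, and it concerns a calcium volume score, whereas 2a concerns plaque progression. The same section reports a randomized comparison of two statins in 615 women, with attained LDL of 94 versus 129 mg/dl and median change of 15.1% versus 14.3%, a gap of 0.8 points. A 32-point gap with patients split evenly would also imply a between-group SD of √(0.25 × 32²) = 16, above the total SDs of 9.5 and 4 that section 13 assumes for the primary endpoint. The cohort figure therefore cannot be set against the plan's 19.7-point effect.

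No numerical size for the gain from adjustment can be drawn from the documents.

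**What to change.** 1. *Laboratory list.* Add a fasting lipid panel and glucose or HbA1c to the section 8.1 panel, run on the existing fasting draws, at least at baseline.
2. *Baseline list.* Itemise diabetes status and the date VKA treatment began among the entry data in section 4.
3. *Wording of 2a.* Replace the open-ended reference to all risk factors with a short prespecified list of baseline covariates, for example age, sex, the baseline value of the plaque measure, smoking, hypertension, diabetes, baseline LDL and statin use. With about 100 patients the list should stay short.
4. *Section 13.* Put the same list in the ANCOVA for 2a. Without this step the model would still contain only demographics and baseline CACS.
5. *Follow-up LDL.* If it is measured at 6 and 12 months, report it by arm descriptively and do not adjust for it.

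The cost is a small assay charge per patient, a few CRF fields, and a text change in two sections. No extra visit or blood draw is needed.

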## Patient Recruitment:

Eligible patients will have atrial fibrillation at enrollment or two or more episodes of atrial fibrillation, as documented by electrocardiography, at least 2 weeks apart in the 12 months before enrollment.

Patients randomized to warfarin will continue their monthly study visits focusing on control of the INR to warfarin clinic, and research study visits every 3 months to include an assessment of clinical outcomes and adverse events. For any patient who is lost to follow-up or withdraws consent, attempts will be made to determine vital status at the end of the trial.

**TIMELINE:** Recruitment will take place over 6 months, follow up for the next 12 months and closeout for 3 months. Entire study duration will conclude in less than 2 years.

**Figure 2.**

Day	What you do
Day 1	
 
You will have routine blood tests done and check your kidney function if needed.
 
You will have a CT scan (without contrast), and a CT angiogram (with contrast) (If you are a female who is able to have children, you will have a urine pregnancy test done before these tests.)
 
For Group 1, continue taking warfarin.
 

	
 
• For Group 2, begin taking assigned study drug once a day for the next 12 months. Keep taking until the end of study, unless told to stop by the study doctor or his staff.
 

3 Months	
 
• For Group 2, get new supply of study drug
 
• For both groups, we will ask you about changes in your health and medications and about visits to the doctor, emergency room or other outpatient clinic (for example, urgent care center).
 

6 Months	
 
• For Group 2, get a new supply of study drug
 
• For both groups, we will take blood for routine blood tests.
 
• For both groups, we will ask you about changes in your health and medications and about visits to the doctor, emergency room or other outpatient clinic (for example, urgent care center).
 

9 Months	
 
• For Group 2, get new supply of study drug
 
• For both groups, we will ask you about changes in your health and medications and about visits to the doctor, emergency room or other outpatient clinic (for example, urgent care center).
 

12 Months	
 
• We will take blood for routine blood tests,
 
• You will undergo a CT scan (without contrast) and CT angiogram (CT scan with contrast). (If you are a female who is able to have children, you will have a urine pregnancy test done before these tests.)
 
• You are done – the study is complete.
 

### Study Endpoints

Events will be recorded. Stroke will be defined as a focal neurologic deficit, from a nontraumatic cause, lasting at least 24 hours and categorized as ischemic (with or without hemorrhagic transformation), hemorrhagic, or of uncertain type (in the case of patients who do not undergo brain imaging or in whom an autopsy is not performed). The rate of myocardial infarction, hospitalization for angina and revascularization will be recorded. The primary safety outcome will be major bleeding, defined, according to the ISTH criteria, as clinically overt bleeding accompanied by a decrease in the hemoglobin level of at least 2 g per deciliter or transfusion of at least 2 units of packed red cells, occurring at a critical site, or resulting in death. Additional safety outcome will be clinically relevant nonmajor bleeding, defined as clinically overt bleeding that does not satisfy the criteria for major bleeding and that led to hospital admission, physician-guided medical or surgical treatment, or a change in antithrombotic therapy. Other safety measures will include any bleeding, other adverse events, and liver-function abnormalities.

The primary and secondary efficacy and safety measures will be adjudicated on the basis of prespecified criteria by a clinical-events committee whose members will be blinded to the study-group assignments.

### B. Laboratory Measurements (0 , 6 and 12 months)

All participants will be instructed to abstain from smoking, alcohol, and food intake, eg, overnight fasting or at least 10 hours before sample drawing. Venous blood samples of all patients will be drawn after admission in a fasting state. Routine blood specimens will be shipped to our

central clinical laboratory to be measured uniformly in a highly standardized center. Blood samples, including CBC, Matrix Gla protein, and INR will be assessed at every visit.

#### **Cardiac multislice computed tomography data acquisition and analysis**

In all patients, a prospective non-enhanced coronary calcium scan will be performed with a 64-slice MSCT scanner (GE 64; GE Healthcare, Milwaukee, WI). For quantitative assessment of coronary artery calcification, the Agatston score will be calculated, using a 3 mm CT slice thickness and a detection threshold of  $\geq 130$  HU involving  $\geq 1$  mm^2 area/lesion (3 pixels).

Cardiac CT angiography will be performed using a collimation of  $64 \times 0.625$  mm and a rotation time of 0.4 s. The tube current will be 400–770 mA (depending on body weight), at 100–120 kV. Contrast material at a flow rate of 5.0 mL/s was administered in the antecubital vein, with volumes depending on the total scan time (60–80 mL). In the absence of contraindications, patients with a heart rate  $\geq 60$  b.p.m. will be administered 50–100 mg metoprolol oral and up to 40 mg metoprolol intravenous. Interpretation will be by expert reading by an experienced cardiologist and a radiologist blinded to all clinical data. Image analysis will be performed on dedicated workstations for post-processing and evaluation.

## **5. ELIGIBILITY-INCLUSION/EXCLUSION**

### **Key Inclusion Criteria:**

1. Eligible patients with atrial fibrillation at enrollment or two or more episodes of atrial fibrillation or flutter, as documented by electrocardiography, at least 2 weeks apart in the 12 months before enrollment
2. Age 18–84
3. On anticoagulation for 6 months prior to enrollment at a stable dose.
4. Willingness to participate in the study and ability to sign informed consent
5. Minimum CAC score of 10

### **Key Exclusion Criteria:**

1. Atrial fibrillation due to a reversible cause, moderate or severe mitral stenosis, or conditions other than atrial fibrillation that require anticoagulation (e.g., a prosthetic heart valve)
2. Prior rivaroxaban use.
3. A need for aspirin at a dose of  $>165$  mg a day or for both aspirin and clopidogrel,
4. Renal insufficiency (serum creatinine level of 12.5 mg per deciliter or calculated creatinine clearance of  $<50$  mL per minute).
5. Serious bleeding event in the previous 6 months or a high risk of bleeding (eg, active peptic ulcer disease, a platelet count of  $<100,000/\text{mm}^3$  or hemoglobin level of  $<10$  g/dL, stroke within the previous 10 days, documented hemorrhagic tendencies, or blood dyscrasias)
6. Weight in excess of 325 pounds
7. Resting hypotension (systolic blood pressure of  $<90$  mmHg) or resting hypertension (systolic blood pressure of  $>170$  mmHg or diastolic blood pressure of  $>110$  mmHg).
8. History of active malignancy requiring concurrent chemotherapy.
9. Any unstable medical, psychiatric, or substance abuse disorder that in the opinion of the principal investigator is likely to affect the subject's ability to complete the study.
10. Known allergy to iodinated contrast material

11. Pregnancy or breast feeding

## **6. TREATMENT**

Patients will be randomized to either stay on warfarin at current doses, managed by the warfarin clinic at Harbor-UCLA with target INR of 2-3 and come in for quarterly visits with INR checks and documented safety; or Rivaroxaban 20 mg once daily.

## **7. PRODUCT INFORMATION**

### Drug ordering and accountability:

Janssen is supplying study drug, and will provide enough medication for the entire study to the research pharmacy. The Research Pharmacy at Los Angeles Biomedical Research Institute will be responsible for packaging and distributing the medications.

The research pharmacy will be responsible for ensuring that the investigational product is stored under the appropriate environmental conditions (temperature, light, and humidity).

